## 7.11 Safety Analysis

Safety will be evaluated by the incidence of treatment-emergent AEs, severity and type of AEs, and by changes from baseline in the patient's vital signs, neurotoxicity assessment, ECGs, and clinical laboratory results. Exposure to study drug and reasons for discontinuation will be tabulated.

These analyses will be performed using the safety population.

### 7.11.1 Adverse Events

AEs will be tabulated according to the Medical Dictionary for Regulatory Activities (MedDRA) Version 19.0 by system organ class, high-level terms, preferred terms and intensity. AEs with missing start and/or end dates will be imputed according rules specified in Section 7.1.3.

Treatment emergent AE is defined as any AE that occurs after administration of the first dose of study treatment and up through 30 days after the last dose of study drug. Patients with the same AE more than once will have that event counted only once within each body system, once within each high-level term, and once within each preferred term. AEs will be summarized and will include the following categories:

- Treatment-emergent AEs
- Drug-related treatment-emergent AEs
- Grade 3 or higher treatment-emergent AEs
- Grade 3 or higher drug-related treatment-emergent AEs
- Treatment-emergent AEs resulting in study drug discontinuation
- SAEs
- AEs of peripheral neuropathy identified by the broad search MedDRA SMQ "Peripheral neuropathy"

Treatment-emergent AEs will be tabulated by system organ class, high-level term and preferred term. The most commonly reported treatment-emergent AEs (i.e., those events reported by  $\geq$  10% of all patients) will be tabulated by preferred term. The individual patient's information on the DLTs will be presented in a listing. Additional analyses of peripheral neuropathy may also be presented.

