Overall response will be evaluated beginning after 2 cycles of therapy. Objective response over the course of the study will be assessed by an IRF according to the IWG Revised Response Criteria for Malignant Lymphoma [1]. Patients, including those who achieve a CR, a PR, or stable disease (SD), may receive brentuximab vedotin for up to 16 cycles. Treatment with brentuximab vedotin beyond 16 cycles may be permitted at the joint discretion of the sponsor and the investigator for those patients experiencing continued clinical benefit. Following administration of the final dose of brentuximab vedotin, patients will be monitored for adverse events for a minimum of 30 days. Patients will be followed for PFS and OS every 12 weeks for 12 months after the EOT visit. Thereafter, assessment for OS will continue every 6 months until the sooner of death or study closure or a maximum of 2 years after enrollment of the last patient. Patients who remain on treatment after Cycle 16 will be followed according to the above schedule or until study closure.

Study drug will be discontinued due to occurrence of unacceptable AE, progressive disease, patient withdrawal, or study termination. Patients may discontinue therapy at any time. Additionally, those patients who experience a CR and are candidates for hematopoietic stem cell transplantation must discontinue brentuximab vedotin prior to chemotherapy and transplant; these patients will be followed for survival analyses until study closure.

AEs will be assessed, and laboratory values, vital signs, and electrocardiograms (ECGs) will be obtained to evaluate the safety and tolerability of brentuximab vedotin.

Serial blood samples for determination of the concentration of brentuximab vedotin, total therapeutic antibody, and MMAE will be obtained during Cycle 1 and subsequent cycles at prespecified time points as described in the Schedule of Events (SOE) in the protocol.

Radiological evaluations, (CT scan or magnetic resonance imaging [MRI], and PET as clinically indicated), will be employed to assess the status of the patient's underlying disease. An evaluation of disease response will be assessed by an IRF according to the IWG Revised Response Criteria for Malignant Lymphoma [1] evaluated at Cycles 2, 4, 7, 10, 13, and 16 and

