### 7.11.2 Clinical Laboratory Evaluations

Descriptive statistics for the actual values of clinical laboratory parameters (and/or change from baseline in clinical laboratory parameters) will be presented for all scheduled measurements over time. Mean laboratory values over time will be plotted for key laboratory parameters.

If a patient has repeated laboratory values for a given time point, the value from the last evaluation will be used.

The parameters to be analyzed are as follows:

- Hematology: hemoglobin, hematocrit, platelet count, total white blood cell (WBC) count, and differential WBC count
- Serum chemistry: blood urea nitrogen, creatinine, total bilirubin, urate, lactate dehydrogenase, gamma-glutamyl-transpeptidase (GGT), phosphate, albumin, alkaline phosphatase, aspartate aminotransferase (AST), alanine aminotransferase (ALT), glucose, sodium, potassium, calcium, chloride, carbon dioxide, magnesium and uric acid
- CCI
- [Redacted]

Shift tables for laboratory parameters will be generated based on changes in National Cancer Institute Common Terminology Criteria for Adverse Events (NCI CTCAE) grades from baseline to the worst postbaseline value.

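### No safety rule marks the start of later chemotherapy or transplant conditioning, so its toxicity can enter the 30-day adverse event tables and the open-ended laboratory shift tables

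*SAP*

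**What the plan says.** SAP Section 7.11.1 treats every AE with onset from the first dose "up through 30 days after the last dose of study drug" as treatment-emergent. The definition has no cut or flag at the start of another treatment. The same section calls for all-causality, drug-related, Grade 3 or higher, Grade 3 or higher drug-related, and serious AE summaries. Section 7.11.1.1 adds a drug-related SAE summary.

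Section 7.11.2 compares CTCAE "grades from baseline to the worst postbaseline value" in the shift tables and gives no last date for a postbaseline value. The by-visit laboratory statistics "will be presented for all scheduled measurements over time", but that restriction is not repeated for the shift tables. Section 7.1 sets inclusion of all available safety data as the default for tabulations.

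Section 4.4 states that "those patients who experience a CR and are candidates for hematopoietic stem cell transplantation must discontinue brentuximab vedotin prior to chemotherapy and transplant" and that "these patients will be followed for survival analyses until study closure". It also states, with no exception for new therapy, that after the final dose "patients will be monitored for adverse events for a minimum of 30 days".

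Section 7.8.2 names other antitumor treatment in the censoring rules for duration of response and PFS. Section 7.11 contains no comparable rule.

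**The concern.** The plan describes a route by which some patients leave the study drug for chemotherapy and transplant, and it deals with other antitumor treatment when it estimates duration of response and PFS. The safety section does not deal with it. If the new treatment begins while AEs are still counted as treatment-emergent, its cytopenias, infections or mucositis fall into the same tables as those of brentuximab vedotin. If laboratory values are still being recorded, one low count after chemotherapy can set a patient's worst grade.

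The trial is open-label with a single agent, so no control arm would show the same excess. Any effect would be concentrated in patients in CR who are transplant candidates. Safety is a phase 1 primary endpoint (Section 5.1) and a phase 2 secondary endpoint (Section 5.5), and some of the summary groups in Section 7.1 are small. Separately, the AE tables stop at 30 days and the shift tables have no stated stop, so the two may cover different periods for the same patient.

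**Working it through.** The plan gives no figure on this point to reproduce. The check sets the definitions side by side and then sizes the effect per patient.

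**Definitions compared**

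| Output | Starts | Ends | Rule for later therapy | Attribution |
|---|---|---|---|---|
| Treatment-emergent AEs: all, Grade 3 or higher, serious (7.11.1, 7.11.1.1) | First dose | 30 days after last dose | None | None in these tables; separate drug-related tables exist |
| Laboratory shift tables (7.11.2) | Baseline | Not stated | None | None |
| Duration of response and PFS (7.8.2) | First response; first dose | Progression or death | Other antitumor treatment named in the censoring rule | Not applicable |

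**When contamination can occur**

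- AE tables: only if the new therapy starts within 30 days of the last dose. Doses are 21 days apart (Section 4.4), so the window runs 30 − 21 = 9 days past the date on which the next dose would have been due. The SAP gives no interval between last dose and chemotherapy.
- Shift tables: only if laboratory values are collected after the new therapy starts. The SAP does not settle this. For patients going to transplant it mentions follow-up for survival analyses only.

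**Size per affected patient**

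Let N be the patients in a summary group, b the number with a qualifying event before any new therapy, and k the number whose only qualifying event follows the new therapy but lies inside the window.

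- Rate as the plan would report it: (b + k)/N
- Rate restricted to the time before new therapy: b/N
- Difference: k/N

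Inputs for N: about 42 patients in total and at least 15 per disease (Section 6.0); at least 10 patients with sALCL in first relapse (Section 6.0), who form their own summary group in Section 7.1; and 36 for all patients at 1.8 mg/kg, taken as 42 minus up to 6 in the 1.4 mg/kg cohort. These are planned evaluable numbers, used here as an approximation to the safety population. The value of k is not in the SAP; 0 to 5 is an assumption for illustration.

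| N | k = 0 | k = 1 | k = 5 |
|---|---|---|---|
| 42 | 0 | 1/42 = 2.4 points | 5/42 = 11.9 points |
| 36 | 0 | 1/36 = 2.8 points | 5/36 = 13.9 points |
| 15 | 0 | 1/15 = 6.7 points | 5/15 = 33.3 points |
| 10 | 0 | 1/10 = 10.0 points | not shown |

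With an assumed Grade 3 or higher rate of 21/42 = 50.0%, k = 1 gives 22/42 = 52.4% and k = 5 gives 26/42 = 61.9%. With 8/15 = 53.3%, k = 1 gives 9/15 = 60.0%.

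The right-hand end of the N = 15 row is an extreme. It needs five patients in one disease group to reach CR, start new therapy within 30 days of the last dose, and have had no earlier qualifying event.

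The table of common AEs uses a threshold of 10% of all patients. Among 42 that means 5 patients (4/42 = 9.5%, 5/42 = 11.9%), so a few patients with events after new therapy could bring a preferred term into it.

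**The case against.** The strongest reply is that a fixed 30-day tail is consistent with the rest of the plan. It matches the AE monitoring period in Section 4.4, the concomitant medication window in Section 7.6 and the on-study death window in Section 7.11.1.3. All-causality tables are meant to include every cause, and the drug-related AE and SAE tables exist to separate them. Laboratory collection may stop at the end-of-treatment visit, in which case the shift tables are already bounded in practice. Nobody may start chemotherapy within 30 days.

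Much of this stands. The 30-day window is not wrong and should stay. The drug-related tables give real protection, though only as far as the causality judgement goes. The laboratory part depends on a collection schedule in the protocol, which was not available to this review.

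A reader might infer that the plan sends patients in CR to transplant, or that conditioning toxicity is bound to inflate the drug's safety tables. The SAP supports neither. Section 4.4 only requires candidates in CR to stop the drug first, and it gives neither their number nor the gap to chemotherapy.

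The reply does not supply an end date for the shift tables. Nor does it separate causes in them: they carry no attribution, and Section 7.1 makes inclusion of all available data the default.

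**Conclusion.** The gap is in the safety definitions. The plan foresees later chemotherapy and transplant, but neither the AE window nor the shift-table window takes account of when that treatment starts, and the shift-table window has no stated end. Toxicity of later therapy can enter the all-causality, Grade 3 or higher and serious AE tables, and the shift tables, under the two timing conditions set out above.

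The effect is 2.4 points per affected patient at N = 42, 2.8 at N = 36 and 6.7 at N = 15, and nothing if no patient is affected. These sizes assume that the patient has no earlier qualifying event and that the safety population is close to the planned numbers. The primary response rate and the sample size do not depend on this point. It is a low-cost improvement to how the safety tables can be read, and does not invalidate the planned analysis.

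**What to change.** **Section 7.11.1.** Keep the 30-day treatment-emergent AE tables as the main presentation. Add a supportive set (all, Grade 3 or higher, serious) limited to events with onset before the earlier of 30 days after the last dose and the start of other antitumor therapy or conditioning. Name conditioning explicitly in the definition of that date, and flag later events in the listings.

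**Section 7.11.2.** End the worst postbaseline value at 30 days after the last dose, so that the laboratory and AE windows agree. Add a supportive shift table that ends at the start of other antitumor therapy or conditioning where that is earlier.

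**Cost.** SAP wording, one derived date per patient, and a few repeat tables with a date filter. The date of other antitumor treatment is already relevant to the censoring rules in Section 7.8.2; whether the start of conditioning is also recorded should be checked in the eCRF. Delayed drug effects that appear after new therapy starts would be visible only in the retained 30-day AE and shift tables, so both versions need to be shown. Any laboratory values later than 30 days after the last dose would leave the shift tables and be seen in the data listings.

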#### 7.11.1.1 Serious Adverse Events

The number and percentage of patients experiencing at least 1 treatment emergent serious AE (SAE) will be summarized by MedDRA (Version 19.0) primary system organ class, high-level term, and preferred term. Drug-related SAE will be summarized similarly.

In addition, a by-subject listing of the SAEs will be presented (the subject listing will contain all SAEs regardless of treatment-emergent AE status).

#### 7.11.1.2 Peripheral Neuropathies

Peripheral Neuropathy (PN) is defined by the peripheral neuropathy SMQ broad search. The incidence of treatment-emergent PN and treatment-emergent treatment-related PN will each be summarized by preferred term and severity. Time to onset, resolution and improvement of PN events will be summarized. Individual plot by preferred term for treatment-emergent peripheral neuropathy (SMQ) will also be presented.

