**Table 7.1 Imputation Rules for Missing AE Start Dates**

Non-missing	Missing	Estimated
Month and Year	Day	
Day of first dose date of STUDY DRUG, if month and year of onset date are the same as month and year of date of first dose.
 
The last day of the month, if the month and year of onset date are before the month and year of date of first dose of STUDY DRUG.
 
The first day of the month, if the month and year of onset date are after the month and year of date of first dose of STUDY DRUG.

Year	Day and Month	
Day and month of first dose date of STUDY DRUG, if the year of onset date is the same as the year of date of first dose of STUDY DRUG.
 
December 31st, if the year of onset date is prior to the year of date of first dose of STUDY DRUG.
 
January 1st, if the year of onset date is after the year of date of first dose of STUDY DRUG.

	Day, Month and Year	Date of first dose of STUDY DRUG

Missing or partial AE stop dates will be imputed according to the following rules. If only the day is missing, use 15th of the month; if both month and day are missing, use June 30th. For a record with a start date and a partial stop date, if the estimated stop date is before the start date, the stop date will not be estimated.

If AE stop date is not missing and AE stop date < estimated start date, let estimated onset date = AE stop date.

All dates presented in listings are recorded dates without imputation.

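### Partial AE start dates are imputed to the earliest post-dose date and then used for peripheral neuropathy timing, so time to onset is biased early for those records

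*SAP*

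**What the plan says.** The SAP plans the neuropathy timing summary in Section 7.11.1.2: "Time to onset, resolution and improvement of PN events will be summarized". It gives no date from which resolution or improvement is counted, and no rule for partial dates. The parent section, 7.11.1, supplies that rule for all AEs: "AEs with missing start and/or end dates will be imputed according rules specified in Section 7.1.3".

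Section 7.1.3, through Table 7.1, treats a partial start date as follows:

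- Day missing, month of first dose: "Day of first dose date of STUDY DRUG, if month and year of onset date are the same as month and year".
- Day missing, later month: "The first day of the month, if the month and year of onset date are after the month and year".
- Day missing, earlier month: "The last day of the month, if the month and year of onset date are before the month and year".
- Day and month missing, year of first dose: "Day and month of first dose date of STUDY DRUG, if the year of onset date is the same as the year". A later year gives January 1 and an earlier year December 31.
- Everything missing: the date of first dose.

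Stop dates follow a different rule in the same section: "If only the day is missing, use 15th of the month; if both month and day are missing, use June 30th". A stop date that would fall before the start is not estimated. A known stop date that precedes the imputed start replaces it. Listings show recorded dates only.

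**The concern.** For onset after first dose, the start-date rule picks the earliest date compatible with what was recorded. That is a cautious choice when the question is whether an event counts as treatment-emergent. It is a poor choice when the date becomes the end point of a time-to-onset measurement, because every error then has the same sign and errors do not average out. A neuropathy known only by the year of first dose is given a time to onset of zero.

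Neuropathy has its own subsection, search definition, timing summaries and individual plots. The trial plans about 42 evaluable patients summarized in seven overlapping groups, so a few artificial onsets at first dose could be visible in a group's quartiles. If recovery is counted from onset, the same early shift carries into it.

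**Working it through.** The SAP gives no figure for neuropathy timing, so there is none to reproduce. The rules were applied to dated examples and to a simple model.

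**1. Dated examples** (first dose 20 March 2013; days from first dose, and days from onset to stop)

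| True onset to stop | Missing | Imputed onset to stop | Time to onset, true / imputed | Recovery, true / imputed |
|---|---|---|---|---|
| 25 Jun to 20 Aug | start day | 1 Jun to 20 Aug | 97 / 73 | 56 / 80 |
| 10 Sep to 10 Nov | start day and month | 20 Mar to 10 Nov | 174 / 0 | 61 / 235 |
| 3 Jun to 30 Aug | both days | 1 Jun to 15 Aug | 75 / 73 | 88 / 75 |
| 10 Jun to 30 Aug | stop day | 10 Jun to 15 Aug | 82 / 82 | 81 / 66 |
| 5 Mar to 10 May | start day | 20 Mar to 10 May | -15 / 0 | 66 / 51 |

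The first two rows show the early shift. The next two show the stop rule shortening recovery. The last is an onset before first dose, which moves later.

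**2. Average shift in onset.** Assumptions, not in the SAP: first dose uniform over a 365-day year; true onset uniform on study days 22 to 336, that is L = 21 to 335 days after first dose (16 cycles × 21 days = 336).

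- *Day missing.* An onset on day d of a later month moves back d - 1 days. Over the year the mean is (7 × 465 + 4 × 435 + 378) / 365 = 5373 / 365 = 14.7 days, maximum 30. Simulation gives 14.7 to 14.8.
- *Day and month missing.* Mean L = 178; mean L² = 178² + (315² - 1)/12 = 39,953.
  - Share in the year of first dose, hence placed on the first dose date: 1 - 178/365 = 51%.
  - Contribution of these: 178 - 39,953/365 = 68.5 days.
  - Contribution of onsets in the next year, set to January 1: (39,953 - 178)/(2 × 365) = 54.5 days.
  - Total: 68.5 + 54.5 = 123.0 days, maximum 335. Simulation gives 123.1 to 123.8.
- *Onset from the day after first dose (L = 1 to 336) instead.* Simulated means are 14 days (day missing), 116 days (day and month missing) and 168 days (wholly missing). No imputed onset is later than the true one; it is unchanged in 3.4%, 0.3% and 0% of cases.

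**3. Recovery counted from onset** (L = 1 to 336; true duration uniform on 1 to 199 days, an assumption)

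| Missing | Longer | Shorter | Mean change |
|---|---|---|---|
| Start day; stop known | 96.6% | 0% | +14.3 days |
| Both days | 84.2% | 13.9% | +13.6 days |
| Start known; stop day | 47.2% | 49.6% | -0.5 days |
| Start day; stop day and month | 68.8% | 30.8% | +48.2 days |

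Percentages and means cover records that keep a stop date; in the last row 22.9% lose it. With only days missing, the systematic part comes from the start rule: the 15th is close to neutral on average. The June 30 rule adds an upward shift of its own (+33.7 days with a known start, among records that keep a stop date).

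**4. Effect on a reported mean.** If a share p of records is affected, mean time to onset falls by p times the shift. The SAP does not give p. For a missing day, p = 10% gives 1.5 days and p = 30% gives 4.4 days. For day and month missing, p = 5% gives 6.2 days and p = 10% gives 12.3 days.

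**The case against.** A reader might infer that onset is always moved earlier and recovery always made longer by the same number of days. The SAP does not support that. Complete dates are untouched. An onset before first dose, in the month or year of first dose, can move later. The stop-date rule shortens some recoveries, and the shift carries over day for day only when the stop date is known. Section 7.11.1.2 does not say that resolution or improvement is counted from onset, so the recovery bias is conditional on that reading. A reader might also take it as stated that Table 7.1 was written for treatment-emergent status. That is a fair inference from anchoring starts, but not stops, to first dose; the SAP does not say it.

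The size can also be challenged. Patients are dosed every 21 days, so losing the month of an on-treatment onset should be unusual. The likelier case, a missing day, costs about 15 days, less than one cycle. The number of partially dated records is unknown, and no shift in a quartile has been shown. The summary is descriptive, in a single-agent open-label study, and the listings let a reader see which dates were partial.

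All of this stands as a limit on the claim. It does not remove the bias: for neuropathy beginning after first dose, the rule can only pull a partial start date earlier, and the SAP has neither an exception nor a sensitivity summary.

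**Conclusion.** The point holds for neuropathy that began after first dose and has a partial or missing start date. For those records time to onset is biased early: about 15 days on average if the day is missing, and about 120 days if day and month are missing, with about half of the latter placed on the first dose date. Recovery, if counted from onset, is biased long on average, but not in every record.

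These sizes rest on uniform first-dose dates, onsets and durations. The effect on the published summaries could be negligible or visible, depending on how many records are partially dated. The change is worth making because it is cheap and the error is one-directional in a planned safety result. The undefined origin of time to resolution and improvement should be settled at the same time.

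**What to change.** Add to Section 7.1.3, with a cross-reference in 7.11.1.2:

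- Start dates imputed by Table 7.1 are used only to assign treatment-emergent status.
- For neuropathy timing, a partial start date is set to the midpoint of the possible interval. The interval runs from the later of the first dose date and the start of the known period, to the earlier of the AE stop date and the end of the known period.
- Events with a wholly missing start date are left out of the timing summaries and their number is reported.
- The origin of time to resolution and of time to improvement is stated.
- The timing summaries are also shown without events that have an imputed start or stop date.

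Under the same assumptions and with a known stop date, the midpoint leaves a mean error of about 0.6 days early (day missing) and 22 days early (day and month missing). In the 10 September example the interval is 20 March to 10 November, 235 days. Its midpoint gives a time to onset of 117 days, against 174 true and 0 under Table 7.1. The midpoint is not exact: a year-only record without a stop date can be placed too late, and the stop-date rule still acts on recovery. The summary without imputed dates covers both.

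The cost is a few SAP sentences, one derived variable and one extra table. The treatment-emergent tables do not change.
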